9.0 STATISTICAL CONSIDERATIONS

9.1 Sample Size and Study Duration

As of Amendment 5A, which now allows crossover upon progression from the nivolumab arm to the nivolumab + axitinib arm, we expect enrollment of approximately 2 patients per month. This is derived from tRCC prevalence, access to treatment centers, and enrollment patterns to date, which should be aided by the crossover.

To reduce the overall sample size from the prior design, we have maintained the same overall study design but changed two design parameters: 1-sided alpha will be increased from 0.05 to 0.15, and the targeted hazard ratio will be reduced from $HR = 0.50$ to $HR = 0.40$. With these changes, 22 PFS events will be required to address the primary objective comparing Arms A and C at the time of final analysis (see [Section 9.2](#)). Allowing that approximately 25% of eligible and evaluable patients may not have experienced a PFS event by the time of the final analysis, the target accrual on this study is 28 patients. To account for an additional estimated 5% of patients who might be found to be ineligible for the study or inevaluable for the primary endpoint at the time of or following study enrollment (e.g., due to randomization to Arm B, no central path review performed, or having central path review confirming a diagnosis other than tRCC), the ceiling accrual will be set to 40 patients, including those patients already enrolled.

If the study accrues to the target accrual without interim stopping for futility, the additional time required to enroll up to this maximum once re-opening under Amendment 5A is estimated to be 14 months. As before, all eligible patients will be followed for 5 years after randomization, and the final analysis will be conducted once the target number of PFS events needed for the final analysis has been reached, or after 2 years of follow-up is obtained for the last patient enrolled, whichever occurs first.

9.2 Study Design

With Amendment 5A, as before, eligible tRCC patients will be randomized to receive either axitinib and nivolumab (Arm A) or nivolumab alone (Arm C) in a 1:1 ratio. The enrolling institutions will assess the initial patient eligibility, including the type of RCC. Randomization will incorporate stratification for age (< 18 years vs. \geq 18 years), and prior systemic therapy for RCC (none, anti-VEGF based therapy, or systemic therapy other than anti-VEGF). Patients may receive their assigned therapy for up to 2 years or 26 cycles of therapy, whichever occurs first, as long as they do not experience either progressive disease as defined by the immune RECIST criteria (see [Section 10.2.5](#)) or unacceptable toxicities. The primary endpoint of this study is progression-free survival (PFS), defined as the time from randomization to the earliest of disease progression (according to RECIST adapted for immunotherapy) or death due to any cause (see [Sections 9.4](#) and [10.2](#)).

In planning the amended 2-arm design of this study, patient-level data on tRCC patients with metastatic disease who would have been eligible for AREN1721 were extracted from three separate cohorts: 7 patients from the cohort described by Ambalavanan and Geller, 15 patients from the cohort described by Malouf et al, and 3 patients from the COG study AREN03B2.^{34,24} PFS for the 3 cohorts was plotted together and found to be in agreement (log-rank test $p = 0.72$; Figure 1A). As such, these data were pooled into a single “historical” cohort used to select an appropriate parametric distribution for PFS in this disease setting from the proportional hazards family of models, from which determinants of power and sample size could be based. Upon superimposing the “best-fit” exponential, Weibull, and piecewise exponential models onto the Kaplan-Meier plot for PFS in the pooled historical cohort, it was determined that the piecewise exponential model offered a practically superior fit warranting the relative increase in model complexity (Figure 1B):

Figure 1A

[figure not shown]
[figure not shown]

Figure 1B

A comprehensive simulation study was then performed, varying the following: the target sample size and maximum number of events required at the final analysis time point, the number and timing of interim analyses for futility, futility stopping strategies (conditional power under the alternative and current HR), and the true underlying hazard ratio (from $HR = 1.0$, the null hypothesis type I error scenario, to $HR = 0.40$, the target alternative hypothesis scenario). For all settings and strategies evaluated in simulations, accrual was assumed to be uniformly distributed as 24 patients per year (as reasoned above, acknowledging that slower than expected accrual will yield greater statistical power than reported here). PFS in the control arm was assumed to follow the piecewise exponential distribution shown in Figure 1B. With 100,000 replicates (simulated trials) used to assess each scenario, we arrived at the following trial design and set of operating characteristics.

The trial will enroll a target of 28 patients to observe 22 PFS events, which are required to achieve at least 80% power to detect a hazard ratio of $HR=0.40$ using a one-sided stratified log-rank test with $\alpha = 0.15$. If stratum-specific sample sizes allow, stratification of the test will include those factors used for stratification at the time of randomization (age and prior systemic therapy).

The trial will include one formal interim analyses for futility, conducted at 50% (11) of the required 22 PFS events. At this time, an observed hazard ratio greater than 1.00 (i.e., a

trend in the wrong direction) will result in early termination of the trial for futility. The simulated percentage change of early stopping for futility at the planned interim analysis (“early futility”), continuing to the final analysis but failing to reach statistical significance (“lack of efficacy”), and continuing to the final analysis and reaching statistical significance (“efficacy”) are tabled below for a range of true underlying hazard ratios. Also presented are the average simulated sample size (“Average N”) and average simulated time from reopening with Amendment 5A to final trial outcome (“Average Remaining Duration”) corresponding to each possible trial outcome. These numbers take into account the patients already enrolled, eligible, and anticipated to be evaluable for the primary endpoint.

True HR	Interim Analysis (50% Events)			Final Analysis (100% Events)			
	Average N	Average Remaining Duration	Early Futility	Lack of Efficacy	Efficacy	Average N	Average Remaining Duration
HR = 1.0	24	9 months	50%	36%	14%	28	17 months
HR = 0.5	25	10 months	15%	19%	66%	28	21 months
HR = 0.4	26	10 months	8%	12%	80%	28	23 months

9.3 Methods of Analysis

Primary Endpoint Analyses

The primary endpoint, progression-free survival, is formally defined in [Section 9.4](#) below. Due to the small size of this trial and the need to preserve alpha-spending for the final analysis, there will be no formal interim analyses of PFS for early efficacy, though this trial will be periodically reviewed by the COG DSMC.

Prospective formal interim analyses for futility will be performed once 50% (11) of the 22 targeted PFS events have been observed. The trial will stop early for futility if, given the data observed to date, the observed hazard ratio for PFS is greater than 1.00, suggesting a trend toward worse outcomes for Arm A (nivolumab + axitinib) compared to Arm C (nivolumab alone).

The final PFS analysis will be performed based on the first quarterly data freeze where at least one of the following criteria are met: (1) a minimum of 2 years of follow-up has been obtained for each patient still “at risk” for a PFS event or (2) when at least 22 PFS events needed for a fully powered final analysis have been confirmed. At this time, a stratified, one-sided log-rank test (using the stratification factors at randomization, age and prior therapy, if stratum-specific sample sizes allow) will be performed to compare treatment arms with alpha = 0.15. A stratified Cox proportional hazards model will also be fit to evaluate the final hazard ratio between the treatment arms (stratification as numbers allow); this will be reported with a 70% confidence interval (to align with the overall alpha level of the primary log-rank test).

While post-progression outcomes on combination therapy among patients who receive crossover upon first progression on the nivolumab-only arm (Arm C) will not be counted toward the primary endpoint analyses, their post-progression experience, including time from first progression to second progression or death (second PFS) will be summarized descriptively.

Secondary Endpoint Analyses

Secondary endpoints OS and ORR (defined in [Section 9.4](#) below) as well as all Grade 3 non-hematologic adverse events and all Grade 4 and higher adverse events will be monitored for data cleanliness and routine reporting as well as formally compared at the time of the final analysis for the primary endpoint, as described below. For ORR and OS below, stratifications factors again may be collapsed and/or omitted depending on the final counts.

ORR: A logistic regression model for overall response, stratified by the stratification factors used at randomization (age and prior therapy) will be fit, including treatment arm as a key covariate. From this model, the odds ratio for treatment arm will be reported with a 70% confidence interval. The ORR observed within each treatment arm will also be reported.

OS: A stratified, one-sided log-rank test (using the stratification factors at randomization, age and prior therapy) will be performed to compare treatment arms with alpha = 0.15. Cox proportional hazards models will also be fit to evaluate the final hazard ratio between the treatment arms, with exploratory modeling taking into account the potential influence of other factors (e.g., baseline disease burden, upfront vs. delayed nephrectomy). From these models, the hazard ratio for treatment assignment will be reported with a 70% confidence interval (to align with the overall alpha level of the primary log-rank test).

AEs: All Grade 3 or higher non-hematologic toxicities and all Grade 4-5 adverse events occurring during protocol therapy or within 100 days of treatment discontinuation, including crossover for patients who receive crossover combination therapy, will be analyzed. The rates of these events will be reported separately by treatment arm (including crossover as a “3rd” arm for this purpose), and both by individual AE and class of AE (e.g., hematologic). Given that some AEs may be rare, Fisher Exact tests will be used to test for statistical significance among any apparent differences by treatment arm.

Exploratory Analyses

Exploratory Aim 1.3.1: To characterize tRCC clinical behavior across all age groups.
We will list and summarize the frequency of site(s) of disease at presentation (including extent of lymph node involvement), site(s) of relapse, surgical practices on protocol therapy, and radiotherapy practices on protocol therapy. We will also summarize the overall response rate (ORR) submitted by the enrolling institution.

Exploratory Aim 1.3.2: To evaluate type of antitumor immune response and stability of T cell activation before and after treatment with immunotherapy or antiangiogenic therapy.
We will summarize the levels of analytes and tumor expression before and after treatment and evaluate the changes due to treatment after logarithmic transformation using the paired t-test. Analytes include myeloid derived stem cells (MDSC): CD45, CD11b, CD33, CD14, CD15, HLA-DR, viability, stain 1; Tregs: viability, CD45, CD4, CD3, CD24, FoxP3; CD8 T cells (CD45, CD8, CD3); CD8 phenotype and activation and exhaustion (CD69, CD38, PD1, CD244, TIM3). Tumor expression of PDL-1, PD1, CD3, CD4 and CD8 will be assessed using TFE RCC samples from the study and scored for intensity (0 – 3).

Exploratory Aim 1.3.4: To characterize the pharmacokinetics of axitinib when given in combination with nivolumab in pediatric patients with tRCC.

The population PK analysis will include all treated patients enrolled beyond Amendment 5A who have at least 1 concentration above the below limit of quantitation (BLQ) in patients treated with axitinib. Pooled PK analysis with another study is to explore the effect of age and body size on axitinib CL/F and Vd/F and make predictions on the dosing of axitinib in pediatric patients in different age groups. Exposure-response relationships will also be explored. The results will be reported separately in a population modeling analysis report. For the purposes of PK analysis, patients who receive crossover therapy will be reported both as a separate cohort and pooled with patients receiving combination therapy up front.

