8.0 CRITERIA FOR REMOVAL FROM PROTOCOL THERAPY AND OFF STUDY CRITERIA

8.1 Criteria for Removal from Protocol Therapy

- a) For Arms A and C, progressive disease of $\geq 40\%$ increase in total tumor burden from baseline or nadir at any time during protocol therapy (see [Section 10.2](#)) (see exception below).
- b) For Arms A and C, progressive disease of $\geq 20\%$ increase in total tumor burden from baseline or nadir that occurs > 12 weeks after start of protocol therapy, except if a patient met the criteria for pseudoprogression in the first 12 weeks and the total tumor burden has subsequently stabilized or decreased with no additional growth (see [Section 10.2](#)) (see exception below).
- c) For Arm B, progressive disease of $\geq 20\%$ increase from baseline or nadir in total tumor burden at any time during protocol therapy (see [Section 10.2](#)).
- d) Response followed by $\geq 20\%$ increase in total tumor burden from the nadir at any time during protocol therapy (see [Section 10.2.5.1](#)) (see exception below).
- e) Appearance of one or more new lesions or unequivocal progression of non-target lesions (see [Section 10.2.5.2](#)) and refer to [Section 10.2.1](#) for exceptions within the first 12 weeks of therapy (see exception below).
- f) Resection of any malignant lesion within the first 12 weeks of protocol therapy (see [Section 13.1.8.1](#)).
- g) Resection of any lesion that is increasing in size at any time while on protocol therapy (see [Section 13.1.8.2](#)).
- h) Completion of planned therapy.
- i) Unacceptable toxicity due to protocol therapy (see [Section 5.0](#)).
- j) Refusal of further protocol therapy by patient/parent/guardian.
- k) Physician determines it is in patient's best interest.
- l) Development of a second malignancy.
- m) Pregnancy.
- n) Repeat eligibility studies (if required) are outside the parameters required for eligibility (see [Section 3.2](#)).

Exception: Patients on Arm C who meet the protocol defined criteria of disease progression prior to Cycle 22 of therapy, may cross-over and receive the remainder of their protocol therapy per Arm A. For those patients who cross-over, the total protocol therapy received on AREN1721 is not to exceed 26 cycles or 2 years, whichever comes first.

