If at the Week 12 assessment the total tumor burden has not yet diminished to $< 20\%$ increase from baseline or nadir, a patient may stay on protocol therapy so long as tumor shrinkage/stabilization continues to occur. If at any point after Week 12 the total tumor burden increases *and* is $\geq 20\%$ from baseline or nadir, this will be defined as progressive disease and the patient must be removed from protocol therapy.

Patients whose best response in the first 12 weeks is pseudoprogression, but who subsequently come off protocol therapy prior to any further assessment, will be considered as having progressive disease. This will include patients who are removed from protocol therapy due to resection of tumor lesions that are increasing in size (see [Section 13.1.8.2](#)).

Note: An increase in tumor size of $\geq 40\%$ at any time will be considered true progression and will result in removal from protocol therapy.

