10.2.5 Response Criteria

10.2.5.1 Evaluation of Target Lesions

IMPORTANT: *All calculations of percentage change in total tumor burden to assess response or progression should fully exclude from consideration any malignant lesions that were surgically resected at any time prior to the latest response assessment.*

Complete Response (CR): Disappearance of all target lesions. Any pathological lymph nodes (whether target or non-target) must have reduction in short axis to < 10 mm.

Partial Response (PR): At least a 30% decrease in the sum of the diameters of target lesions, taking as reference the baseline sum diameters.

Progressive Disease (PD): At least a 20% increase in the sum of the diameters of target lesions, taking as reference the smallest sum on study (this includes the baseline sum if that is the smallest on study). In addition to the relative increase of 20%, the sum must also demonstrate an absolute increase of at least 5 mm. See [Section 10.2.1](#) for exceptions during the first 12 weeks.

At least a 40% increase in the sum of diameters of target lesions at any time during the study, taking as reference the smallest sum measured on study (this includes the baseline sum if that is the smallest on study).

Appearance of one or more new lesions is also considered progression. See [Section 10.2.1](#) for exceptions during the first 12 weeks.

For patients who achieve a CR, either due to protocol therapy or surgical resection of any remaining malignant lesions, occurrence of a new lesion ≥ 10 mm or the short axis of a lymph node increasing to ≥ 15 mm at any time is considered PD.

An initial response (any decrease in tumor size) followed by growth of at least 20% (relative to the nadir) at any time is considered PD.

Patients who are removed from protocol therapy for resection of lesions that are increasing in size (per [Section 13.1.8.2](#)) will be considered to have PD at the time of tumor resection.

Stable Disease (SD):

Neither sufficient shrinkage to qualify for PR nor sufficient increase to qualify for PD, taking as reference the smallest sum diameters while on study.

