10.2.5.3 Evaluation of Best Overall Response

The best overall response is the best response recorded from the start of the treatment until disease progression/recurrence (taking as reference for progressive disease the smallest measurements recorded since the treatment started). The patient's best response assignment will depend on the achievement of both measurement and confirmation criteria.

For Patients with Measurable Disease (i.e., Target Disease)

Target Lesions	Non-Target Lesions	New Lesions	Overall Response	Best Overall Response when Confirmation is Required*
CR	CR	No	CR	≥ 4 wks. Confirmation**
CR	Non-CR/Non-PD	No	PR	≥ 4 wks. Confirmation**
CR	Not evaluated	No	PR	
PR	Non-CR/Non-PD/not evaluated	No	PR	
SD	Non-CR/Non-	No	SD	documented at least

	PD/not evaluated			once ≥ 4 wks. from baseline**	
PD	Any	Yes or No	PD	no prior SD, PR or CR	
Any	PD***	Yes or No	PD [#]		
Any	Any	Yes	PD [#]		
* See RECIST 1.1 manuscript for further details on what is evidence of a new lesion. ** Only for non-randomized trials with response as primary endpoint. *** In exceptional circumstances, unequivocal progression in non-target lesions may be accepted as disease progression. # See Section 10.2.1 for exceptions for pseudoprogression during the first 12 weeks of protocol therapy.					
Note: Patients with a global deterioration of health status requiring discontinuation of treatment without objective evidence of disease progression at that time should be reported as " symptomatic deterioration ." Every effort should be made to document the objective progression even after discontinuation of treatment.					

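### No tumour reference is set for second progression after cross-over, so 10.2.5.1 applied as written can count an unchanged tumour as progression again

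*Combined protocol and SAP*

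**What the plan says.** Section 9.3 keeps post-cross-over outcomes out of the primary analysis but commits to reporting them, "including time from first progression to second progression or death (second PFS) will be summarized descriptively". Neither 9.3 nor 9.4 defines second progression.

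The size rules are these:

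- 8.1(a) removes Arm A and C patients for a 40% "increase in total tumor burden from baseline or nadir at any time during protocol therapy". 8.1(b) does so for 20% after 12 weeks, and 8.1(d) for 20% above nadir after a response.
- 10.2.5.1 sets progression at 20% above the smallest sum on study, where "the sum must also demonstrate an absolute increase of at least 5 mm". It also sets it at 40% at any time, "taking as reference the smallest sum measured on study".
- 10.2.4 ties baseline imaging to the start of treatment. 10.2.6.1 refers to the smallest measurements since treatment started.

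For cross-over, 8.1 adds an exception: an Arm C patient who progresses before Cycle 22 "may cross-over and receive the remainder of their protocol therapy per Arm A". Sections 4.1, 4.3.2, 15.1.2 and 16.2.1 restart the cycle count, the imaging schedule and PK sampling from the first combination cycle. None of them restarts the tumour reference.

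**The concern.** A patient who crosses over because target lesions grew is, by definition, already at least 20% above the smallest sum on study. If that sum remains the reference, the same tumour at the same size satisfies the rule again at the first combination scan. Second PFS would then record disease that is stable on the combination as a second progression. The same criteria govern removal from protocol therapy, so the ambiguity reaches treatment as well as a summary table. Sites could also apply different references. Section 2.6 gives learning about tolerance, response and survival after cross-over as a reason for allowing it, and that purpose needs a consistent definition.

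**Working it through.** The plan gives no figure of its own to reproduce here. The check applies the written rule to assumed tumour sums.

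**Inputs.** N is the smallest target-lesion sum on study, g the proportional growth above N at cross-over, and S = (1+g)N the sum at cross-over. The 20%, 5 mm and 40% conditions come from 10.2.5.1.

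**Threshold.** Progression holds at or above T = min(max(1.2N, N + 5 mm), 1.4N). The cap at 1.4N is there because the 40% rule carries no 5 mm condition. For N of 25 mm or more, 20% of N is at least 5 mm, so T = 1.2N.

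**Shrinkage from the cross-over scan needed to leave the progression range.** The fall must exceed 1 − T/S, which for N of 25 mm or more is 1 − 1.2/(1+g).

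| N | g | T/S | Fall must exceed |
|---|---|---|---|
| ≥ 25 mm | 20% | 1.2/1.2 | 0% (any decrease) |
| ≥ 25 mm | 25% | 1.2/1.25 | 4.0% |
| ≥ 25 mm | 40% | 1.2/1.4 | 14.3% |
| ≥ 25 mm | 60% | 1.2/1.6 | 25.0% |
| 20 mm | 40% | 25/28 | 10.7% |
| 20 mm | 60% | 25/32 | 21.9% |
| 15 mm | 40% | 20/21 | 4.8% |
| 15 mm | 60% | 20/24 | 16.7% |

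The 5 mm condition softens the effect for small sums but does not remove it.

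**Worked case.** Nadir 50 mm, cross-over at 70 mm (g = 40%).

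- Original reference: progression from 1.2 × 50 = 60 mm. A scan at 68 mm is 2.9% smaller than at cross-over, but 36% and 18 mm above nadir, so it is progression.
- Reference reset at cross-over: progression from 1.2 × 70 = 84 mm, so 68 mm is stable. If the 12-week allowance in 10.2.1 also restarted, growth short of 1.4 × 70 = 98 mm could be tolerated in that window when its clinical conditions are met.

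**A larger reduction can still fail.** Nadir 50 mm, cross-over at 90 mm, later scan 63 mm. The tumour has shrunk by 1 − 63/90 = 30%, yet it is 26% and 13 mm above nadir. That is progression as written.

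**Does the existing 12-week allowance help?** It runs from the start of protocol therapy, and nothing restarts it. The first scheduled scan is after Cycle 2 (2 × 4 = 8 weeks). A patient who crosses over then has the next scheduled scan two combination cycles later, no earlier than week 16.

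**Scope.** The target is 28 patients randomised 1:1, so about 28/2 = 14 are on Arm C. Only those who progress on target lesions before Cycle 22 and cross over are covered by this arithmetic, and cross-over exists only since Amendment 5A.

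**The case against.** The strongest reply is the 8.1 exception. Criteria (a), (b), (d) and (e) all point to it, and removing a patient at the first combination scan for the growth that allowed cross-over would defeat it. Section 9.3 distinguishes first from second progression, and 2.6 cites treatment beyond progression. The plan also handles cross-over as a new treatment period, with a new Cycle 1, restarted imaging and PK timing, and a separate column for adverse events. All of this stands. A reset may well be what was intended, and counting the old growth again is not the only literal reading. A reader might infer that the protocol obliges sites to stop the combination in stable patients. The documents do not support that. They leave the reference unstated, and one available rule gives that result.

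The exception still does not close the gap. It excuses the first progression and says nothing about the next. If it waived those criteria for good, no size-based stopping rule would remain.

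A second reply is that 10.2.1 requires growth: "If at any point after Week 12 the total tumor burden increases" and is at least 20% above baseline or nadir. That sentence belongs to the pseudoprogression section, and the matching carve-out in 8.1(b) covers only patients who met the pseudoprogression criteria in the first 12 weeks. Neither is extended to cross-over. The note ending 10.2.1 also treats 40% growth at any time as true progression, so an unchanged 70 mm sum in the worked case would still count.

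A third reply is that the analysis can be repaired. Diameters are recorded at each imaging time point (10.2), second PFS carries no test, and it can be recalculated. That is right for the summary. Combination therapy stopped too early cannot be restored.

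**Conclusion.** The point holds as an undefined reference with a concrete consequence under one written rule. Where 10.2.5.1 is applied as written to a patient who crossed over on target-lesion growth, an unchanged sum is progression again. The shrinkage needed to avoid this exceeds 4.0%, 14.3% and 25.0% at growth of 25%, 40% and 60% (nadir sums of 25 mm or more). The tumour sums and growth values are assumptions, because the documents give neither a distribution of growth at progression nor a cross-over rate. Patients whose first progression was by new or non-target lesions are outside this arithmetic.

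The reach is small: a descriptive outcome, and removal from combination therapy, in a subset of about 14 patients. Three larger conclusions are tempting and unsupported.

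- *The primary comparison is affected.* It is not. Post-cross-over outcomes are excluded (2.6, 9.3), so primary PFS, alpha, sample size and the futility rule stand.
- *A planned response analysis is wrong.* Partial response is indeed defined as "At least a 30% decrease in the sum of the diameters of target lesions, taking as reference the baseline sum diameters", and best overall response stops at progression. But 9.3 and 9.4 plan no response rate after cross-over.
- *A known number of patients would be misclassified.* The stable-disease rates in 2.2.3 (33% and 35%) come from other RCC patients on other combinations and cannot supply that count.

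It is worth correcting because treatment is involved and the correction costs little.

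**What to change.** In 8.1, 9.3 and 10.2.5, state for patients who cross over:

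1. The last tumour assessment on or before the first axitinib dose, normally the first-progression scan, is the new baseline and starting nadir.
2. Lesions on that scan are re-listed as target or non-target, so only lesions appearing later count as new.
3. Second progression and the 8.1 removal criteria are judged against this reference.
4. Whether the 12-week allowance for 20–40% growth in 10.2.1 restarts with combination therapy. Without this the reset threshold is itself unsettled (84 or 98 mm in the worked case).
5. The second-PFS clock still starts at first progression, as 9.3 has it.

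No mandatory repeat scan should be added, since the first-progression scan normally serves. The cost is a few sentences. The one drawback arises when axitinib is delayed and a later scan becomes the reference: growth between first progression and that scan is then not counted, although the time is.
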